11.5. Reporting Adverse Events

11.5.1. Adverse Events

All adverse events, including both observed and volunteered problems, complaints, signs or symptoms, and any death occurring while on study are to be recorded (whether or not the event is related to vaccine administration). The duration and intensity of the event as well as whether or not the event might be associated with the study medication or other causes will be evaluated.

The severity of each adverse event will be graded according to the common toxicity criteria of the AIDS Clinical Trials Group (ACTG) as listed in [Appendix 2](#). When intensity changes occur more frequently than once a day, the maximum severity for the event should be listed. If the intensity category changes over a number of days, then these changes should be recorded separately, having distinct onset and stop dates for each grade.

If the investigator has evidence that the adverse event is not caused by the vaccine, and after consultation with the study Principal Investigator, then the study vaccine may be continued. All adverse events, irrespective of causality, must be recorded in the CRF. All changes in study regimen must be accurately recorded on the study drug pages of the CRF. All adverse events occurring during the trial must be evaluated by the investigator and graded according to the adverse experience grading table ([Appendix 2](#)). **Any serious adverse event (including death) due to any cause must be reported immediately to the principal investigator and the sponsor.** The decision to remove a patient for an adverse event, whether laboratory or clinical, will depend on the severity of the event and its relation to the vaccine and study requirements and therefore, will require judgment. The guiding principal will be to insure the safety of participants and integrity of the study. It is expected that all vaccine related grade 4 events will require discontinuation as will most grade 3 events. Vaccines will be discontinued for any Grade event or at the discretion of the investigator or wish of the volunteer. If a volunteer is withdrawn due to an adverse event follow-up will be conducted as outlined in [Section 6.1.1.7](#).

11.5.2. Serious Adverse Events

All SAEs (related and unrelated) will be recorded while on study protocol. Any SAEs considered possibly or probably related to the investigational product and discovered by the Investigator at any time after the study should be reported. All SAEs must be reported to the Institute of Human Virology through the Medical Monitor within one business day of the first awareness of the event. The Investigator must complete, sign and date the SAE pages, verify the accuracy of the information recorded on the SAE pages with the corresponding source documents, and send a copy by fax to the Institute of Human Virology. If a volunteer is withdrawn due to a serious adverse event, follow-up will be conducted as outlined in [Section 6.1.1.7](#).

Additional follow-up information, if required or available, should all be faxed to the Institute of Human Virology within one business day of receipt and this should be completed on a follow-up SAE form and placed with the original SAE information and kept with the appropriate section of the CRF and/or study file.

The Institute of Human Virology is responsible for notifying the relevant regulatory authorities of certain events. It is the Principal Investigator's responsibility to notify the IRB of all SAEs that occur at his or her site. Investigators will also be notified of all unexpected, serious, drug-related events (7/15 Day Safety Reports) that occur during the clinical trial.

11.6. Data Safety Monitoring Board

The Clinical Research Unit is experienced in establishing DSMBs in single-site protocols in the participation in single and multi-site clinical trials. Adverse Event Reporting requirements of the IRB, FDA, the NIH Biotechnology Activities, and the industry/private sponsor will be followed. For this trial, IHV has established a DSMB. The DSMB plan will be approved by the IRB prior to implementation.

The Data Safety Monitoring Board (DSMB) will review this trial for safety beginning with the enrollment of the first volunteer into the study. The Board will meet prior to advancement to the next higher dose group as outlined in the protocol to insure that there are no safety concerns. It will also meet approximately every 3 months but can be called together on an ad-hoc basis if a particular patient event calls for immediate attention. At the regularly scheduled (3 month) meetings and the advancement to the higher dose group meetings, the board will review the following:

- All Adverse Events
- Update on all Serious / Study Related Events
- All safety related amendments
- Protocol deviations / exceptions
- Laboratory tests, enrollment numbers, clinical summaries
- Require changes in Standard Operational Procedures for Adverse Events Reporting and Chart Audit as necessary.

All reviews will be of blinded data. However, the DSMB will have access to the envelopes with the treatment assignment of the volunteers to unblind the data should this be needed to ensure the safety of study participants. The DSMB may recommend or mandate changes to the study, and has the power to halt the study if it feels that a volunteer's safety is compromised. The DSMB will provide the Principal Investigator, with a written report detailing its review of the study. The investigator(s) will have the opportunity to respond to the DSMB's report.

Board members will be notified of all internal serious study related, drug related, and/or device related Adverse Events in this study within 48 hours of occurrence via email. Each board member should respond via e-mail, or fax within 48 hours.

A DSMB member who is a physician will be called upon via fax, e-mail, or phone call to discuss any deviations/exceptions a PI may be thinking of requesting prior to approaching the sponsor. This will help to determine if the deviation/exception is necessary and will not compromise the safety of the patient.

The IHV DSMB will have at least 4 members not including the Medical Monitor. The DSMB will actively monitor the trial. The members of the Board will not be directly involved with the execution of this study, have conflicts of interest with the conduct of this study, or with study personnel. The Board will be composed of at least the following members:

1. A Statistician
2. At least two physician-investigators

DSMB includes the following members: [name] MD from Johns Hopkins SOM who will also serve as committee Chair; [name] MD from the University of Maryland SOM; [name] MD from the University of Maryland SOM; [name] MD (Medical Monitor) from the University of Maryland SOM; and [name] PhD from Johns Hopkins SOM (statistician).

12. Assessment of Immunogenicity

12.1. Endpoint Evaluations of Immunogenicity

12.1.1. Immunogenicity Endpoint

The primary evaluation of immunogenicity will consist of the generation of antibodies to FLSC as determined by antibody titration using FLSC as the detection antigen. A positive vaccine response will be defined as a 4-fold increase in antibody directed against native FLSC protein by ELISA. In addition geometric mean antibodies titers will be assessed and compared among groups.

12.1.2. Secondary Immunogenicity Endpoints

The secondary evaluation of immunogenicity will include the generations of antibodies to gp120 and human CD4, components of FLSC, determined by antibody titration using gp120 and human CD4 as the detection antigen.

12.1.3. Exploratory/Developmental Immunogenicity Endpoints

1. Antigen-specific CD4+ T cell responses measured by peptide stimulated intracellular cytokine production coupled with surface markers to identify CD4+ T cell subsets, particularly those of the T-follicular helper cell lineage.
2. Assess the presence of neutralizing antibodies;
3. Antibody-Dependent Cellular Cytotoxicity activity;
4. To assess and compare the induction of T-helper and cytotoxic T-lymphocyte activity by ELISPOT and intracellular cytokine staining;
5. Additional developmental assays might be performed on de-identified specimens for antigen-specific B cell responses based on emerging literature

12.2. Immunogenicity Assays

12.2.1. Endpoint Assay

ELISA based assay using FLSC protein will be used. A positive vaccine response will be defined as a 4-fold increase in antibody directed against native FLSC protein by ELISA.

The human serum samples collected before and after immunization will be analyzed, after a 1 hour heating step at 60°C, for the presence of anti-FLSC_I antibodies (total IgG) by the ELISA technique. To determine whether the development of anti-FLSC antibodies is really linked to a specific immune stimulation following vaccination and not to a general immune activation, all sera will be also tested against an irrelevant HIV antigen, p24, that is not cross-reactive with FLSC. In this case, the titers against p24 should remain constant. The results will be expressed as half-maximal antibody titers in arbitrary units (log).

The ELISA assays will be conducted as follows: 6 to 12 serial three-fold dilutions of the serum samples, starting at 1/10, will be tested in 96-well ELISA plates pre-coated with the antigen of interest (*ie* FLSC or p24). The presence of specific antibodies will be revealed by addition of an anti-human total IgG peroxidase-conjugate, followed of a chromogenic hydrogen peroxide-specific substrate. Finally, each well will be read by an automatic plate reader at an optical density (OD) of 450-650 nm.

The background will be given by the blanks (*ie* 6 to 12 wells with all the reagents except sera) which OD values should not exceed 0.2 in average. The OD values from all samples will be subtracted from this mean blank OD. One negative control, a serum from an HIV-negative volunteer, will be present on each ELISA plate. Its OD value, subtracted from the mean blank OD, should not exceed 0.2 at the lowest dilution (1/100).

Two anti-FLSC (or anti-p24) human sera will be on on each ELISA plate: one, with a predetermined antibody titer (see below*), will serve as the standard: *ie* all sample titers will be calculated from the regression curve of this standard ($OD = f(\text{inverse dilution})$) using the SoftMaxPro software (Molecular Devices). The second positive serum will be used as the positive control: its mean titer (m) and the corresponding standard deviation (sd), will have to be calculated from the standard after several independent experiments. The assay will be considered as valid if the titer of this positive control measured on the ELISA plate is included in the titer range: $m \pm 3 \text{ sd}$ (log).

*The titer of the standard will predetermined in several independent experiments: it will represent the average of the values obtained after all these experiments, each value being the inverse serum dilution giving an OD of around 1 (subtracted from the mean blank OD).

The person responsible for the ELISA assays will be [name], at Profectus BioSciences.

12.2.2. Secondary Endpoint Assay

ELISA based assay using gp120 and soluble human CD4 will be carried out as described in [Section 12.2.1](#).

12.2.3. Developmental Assays

1. Antigen-specific CD4+ T cell responses will be measured by peptide stimulated intracellular cytokine production coupled with surface markers to identify CD4+ T cell subsets, particularly those of the T-follicular helper cell lineage. These responses will be assessed by culturing 3×10^6 PBMC in 1 mL of R10 medium containing brefeldin A (10 ug/mL) in the absence or presence of FLSC peptide pools (15mers overlapping by 11 residues), or 1 ug/mL SEB (Sigma) for 6 hours. Cells will be surface stained with titrated amounts of anti-CD3, anti-CD4, anti-CD27, anti-CD45RO, anti-CCR7, anti-CXCR5, anti-CD150, anti-CCR6, anti-PD-1 and anti-CD19 antibodies. The surface-stained cells will be permeabilized (Cytotfix/Cytoperm kit; BD Biosciences) and stained with anti-IFN- γ , anti-IL-2, anti-IL-17a, anti-IL-21 and anti-CD154 antibodies. Events will be collected on a FACSFortessa equipped with four lasers and a high-throughput module. Electronic compensation will employ antibody capture beads (BD Biosciences) and the data analyzed using FlowJo, Version 10.6.
2. Assess the presence of neutralizing antibodies by TZM-bl cells ([Seaman, Janes et al. 2010](#)) and A3R5 assays ([Sarzotti-Kelsoe, Daniell et al. 2014](#)).
3. Antibody-dependent Cellular Cytotoxicity activity (ADCC);
4. To assess and compare the induction of T-helper and cytotoxic T-lymphocyte activity by ELISPOT and intracellular cytokine staining;
5. Additional developmental assays might be performed on de-identified specimens for antigen-specific B cell responses based on emerging literature

12.2.4. Assay Timepoints

The scheduled assay timepoints are detailed in [Table 4](#).

12.2.5. Data Analysis

Immunogenicity parameters will be compared using response and non-response as well as mean medium and geometric mean titers between vaccine recipients and placebo recipients (i.e. Arms 1 and 2 compared to Arm 3) as determined by Student's T test *and chi-square analyses*. Immunogenicity parameters will be compared between FLSC in Arms 1, 2, and 3 as well as between the placebo recipients (Arms 1 to 3 and 2 to 3). Exploratory analyses will be performed (e.g., examination of frequency distributions, modality of distributions, kurtosis and skewness, etc.) for all variables collected before subjecting the values to statistical analysis. Cross-sectional parametric and non-parametric analyses will be conducted on variables exhibiting normal and non-normal distributions, respectively, to examine differences and trends among treatment categories.

The dose selected will be that which provides the optimal CD4i epitope immunogenicity and antiviral activity and safety profile. Based on our results in macaques, we believe that the FLSC will be safe even when administered at the highest dose of 300 µg. Titers will be evaluated for normality (Kolmogorov-Smirnov test) then compared via a parametric test such as one-way analysis of variance (ANOVA). If the data fails the normality test we will use the Kruskal-Wallis test (3-group comparison) and Wilcoxon rank-sum test (2-group comparison) to compare groups. A p value < 0.05 will indicate that one of the vaccination regimens elicits significantly higher response in that measure versus the others.

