4.2. Trial Design Overview

This study is designed to evaluate the safety of the IHV01 vaccine and will be a randomized, placebo-controlled, modified double-blinded dose escalation study in 60 healthy adult volunteers. Although there is a great deal of experience with protein vaccines, the optimal dose of IHV01 given intramuscularly is not known. Therefore, this trial is designed as a dose escalation trial in order to determine the optimal dose to move forward with in future clinical trials. This dose will be chosen after reviewing the safety and immunogenicity data from this trial. Alum has been chosen as an adjuvant due to the extensive amount of safety data available. The study will have 3 arms including placebo, 75 µg dose, 150 µg dose, and 300 µg dose and will last for 336 days (48 weeks). Volunteers will be immunized on Day 0, Day 28(4 weeks), Day 56(8 weeks), and Day 168(24 weeks). Each dose group will have 15 vaccine and 5 placebo recipients. The dosage schedule in this trial was based on the animal data and data with other envelope protein vaccines, and is patterned after the schedule utilized in the RV144 trial in Thailand. From this trial, an optimal dose of the candidate vaccine will be chosen for use in future trials. It is anticipated that the trial will be enrolled and completed 18 months after it is open to enrollment.

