6. INVESTIGATIONAL PLAN

6.1. Overall Study Design

This will be a randomized, placebo-controlled, modified double-blinded study in 60 healthy adult volunteers. The study will evaluate the safety and immunogenicity of the full length single chain (FLSC) gp120-CD4 complex vaccine formulated with alum at three different doses. The study will have 3 arms as outlined below in Figure 1 and will last for 336 days (48 weeks). Volunteers will be immunized on Day 0, Day 28(4 weeks), Day 56(8 weeks), and Day 168(24 weeks).

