8.4. Randomization and Blinding

Volunteers will be randomized using block randomization in a 3:1 ratio of FLSC:placebo. They will be block randomized in groups of 4 with each study group. This will be done by the research pharmacist utilizing random # generator called Stat Trek. There will be 5 groups of 4 volunteers in each randomized block (each block will have 3 FLSC recipients and 1 placebo recipient).

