8.5. Identification of participants as volunteers in HIV vaccine trial

All volunteers will receive an individual identification card indicating their status as an HIV-1 vaccine trial participant. All volunteers will be counseled periodically regarding the potential for testing positive on routine screening tests for HIV-1 as a consequence of participation in this trial and receiving these vaccine products. All volunteers will be offered further confirmatory testing and certification as to the nature of their vaccine trial participation whenever needed to address complications arising at home, at work or in the community that could arise from routine screening from HIV-1.

8.6. Detection of inter-current HIV-1 infections.

Each volunteer will be counseled at each visit and an algorithm followed to identify inter-current HIV-1 infections. The algorithm is shown in [Figure 1](#) and uses FDA approved serological and nucleic acid diagnostic kits at each step. If an individual is determined to have an inter-current infection with HIV-1 they will be excluded from further immunizations and counseled about their medical options. Enrollment in the trials does not include subsequent care for an inter-current HIV-1 infection. The volunteer will be counseled on how to access that care if they choose to do so.

Figure 1: Algorithm to detect inter-current HIV-1 infections

[figure not shown]

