9.4.3. FLSC 300 ug (Group 3)

Before injection, the FLSC vial will be removed from the refrigerator and swirled until a uniform solution results. Once the FLSC is in a uniform solution, 1.0 ml (300ug) of FLSC will be withdrawn from the vial using a 22-25 gauge, 25 mm (1 inch) needle with a 1-mL sterile disposable syringe. The syringe will then be covered with a film/aluminum foil to prevent visualization of the product.

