9.4.4. Placebo (Groups 1-3)

Before injection, depending on the group (see [Table 7](#)), the saline will be withdrawn using a 22-25 gauge, 25 mm (1 inch) needle with a 1-mL sterile disposable syringe. The syringe will then be covered with a film/aluminum foil to prevent visualization of the product.

Table 7: Placebo Groups

Group Number	Volume of Saline
1	0.25 ml
2	0.5 ml
3	1.0 ml

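### Sections 12.2.5 and 13.5 misstate three parts of the secondary immunogenicity analysis: the vaccine-placebo contrast, the meaning of p<0.05 across doses, and the test to be used

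*Combined protocol and SAP*

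**What the plan says.** **Design.** Section 4.2 states: "Each dose group will have 15 vaccine and 5 placebo recipients". Table 3 gives the same split. Section 8.4 randomizes 3:1 within each group, and "each block will have 3 FLSC recipients and 1 placebo recipient". Group 3 is the 300 ug group (section 9.4.3), and saline is prepared for all three groups (section 9.4.4).

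**Contrast.** Section 12.2.5 compares titers and response "between vaccine recipients and placebo recipients (i.e. Arms 1 and 2 compared to Arm 3", closing the parenthesis there. Its next sentence places FLSC in Arms 1, 2 and 3. It then adds a comparison of placebo recipients, labelled only by pairing Arm 1 with Arm 3 and Arm 2 with Arm 3. Sections 13.2 and 13.5 state the vaccine-placebo contrast without arm numbers: dose groups with each other, and each with placebo.

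**Tests.**
- 12.2.5: t test and chi-square. For titers, ANOVA after a normality check; if that fails, Kruskal-Wallis for three groups and Wilcoxon rank-sum for two.
- 13.2: t test and chi-square.
- 13.5: Wilcoxon matched-pairs or Sign test, with Fisher's exact test.

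**Meaning of p.** Section 12.2.5 ends by reading p<0.05 as showing that one vaccine regimen produces a higher response than the others. Section 13.6 says a significance level is not pertinent, although section 13.4 sets a 5% Type I error for the safety comparisons.

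**Arm labels.** Section 4.2 says "The study will have 3 arms including placebo" and then lists placebo and three doses. Section 6.1 says "The study will have 3 arms as outlined below in Figure 1", but the only Figure 1 is captioned "Figure 1: Algorithm to detect inter-current HIV-1 infections".

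**The concern.** Three instructions cannot be followed as written.

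1. The parenthesis in 12.2.5 treats Arm 3 as the placebo arm. Arm 3 can only be the 300 ug group, with its own placebo recipients.
2. An overall test across three doses is given a conclusion that it cannot deliver.
3. A paired test is assigned to two independent groups.

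These are secondary analyses, but section 4.2 says the dose for later trials will be chosen after review of the safety and immunogenicity data. What the immunogenicity report may claim about one dose over another therefore matters. Three sections naming different tests for one contrast also leave the method open until the data have been seen.

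**Working it through.** **Inputs.** From the documents: 15 FLSC and 5 placebo per group, three groups, allocation 3:1 in blocks of four. The plan gives no means, SDs or response rates for human titers, so those used below are assumptions. It also has no power figure for immunogenicity. The only power figures are the detectable SAE rates in section 13.1 (73.5% within group, 36.8% pooled). A two-sided, continuity-corrected two-proportion formula with a control rate of 0.1% gives 73.4% and 36.7%, so they reproduce. This point does not affect them.

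**Step 1: what the parenthesis compares if taken literally.**

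| Side | FLSC | Placebo | Total | Placebo share |
|---|---|---|---|---|
| Arms 1 and 2 | 30 | 10 | 40 | 25% |
| Arm 3 | 15 | 5 | 20 | 25% |

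Let m1, m2, m3 be the mean log titers of vaccinees in the three groups and m0 the placebo mean, taken as equal across groups. The expected difference is

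(15·m1 + 15·m2 + 10·m0)/40 − (15·m3 + 5·m0)/20 = 0.75 × [(m1 + m2)/2 − m3].

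The placebo mean cancels. What remains is a diluted comparison of the two lower doses with the highest.

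- Simulation with the same vaccine effect at every dose (assumed 2, 3 or 5 SD; 5,000 trials each): the literal contrast rejects in 0.7%, 0.04% and 0% of trials.
- If every vaccinee responds and no placebo recipient does, the literal contrast is 30/40 against 15/20, Fisher p = 1.0. The true vaccine-placebo contrast is 45/45 against 0/15, p = 1.9 × 10⁻¹⁴.

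**Step 2: what p<0.05 from the three-dose test shows.** The null hypothesis is that the three doses are alike. Rejecting it says that they are not all alike, and nothing about which dose differs. Simulation: 20,000 trials per pattern, 15 per dose, normal log10 titers, SD 0.5.

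| Assumed log10 means, lowest to highest dose | ANOVA p<0.05 | Kruskal-Wallis p<0.05 |
|---|---|---|
| 0 / 0.6 / 0.6 (no single highest dose) | 92.0% | 90.0% |
| 0 / 0.3 / 0.6 | 81.4% | 78.9% |

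In the first pattern the sentence in 12.2.5 gives a false conclusion in about nine trials of ten. In the second, the truly highest dose ranks top in 96% of significant ANOVA trials (94% to 98% for SD 0.6 to 0.4). However, the top-ranked dose is separately above both others by unadjusted t tests in only 42% of them (37% to 53% for SD 0.6 to 0.4).

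**Step 3: pairing.** A matched-pairs or Sign test needs one placebo partner for each vaccinee. There are 45 vaccinees and 15 placebo recipients, each block holds three of one and one of the other, and no section defines partners. Both tests fit a volunteer's change from before to after immunization, but that is not a comparison with placebo.

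**Step 4: what a pairwise statement can support.** The 95% interval half-width for two doses is t(0.975, 28 df) × SD × √(2/15). At SD 0.5 this is 2.048 × 0.5 × 0.365 = 0.374 log10, or 2.4-fold. Over SD 0.4 to 0.6 it runs from 0.299 to 0.449 log10, or 2.0- to 2.8-fold.

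**The case against.** The strongest reply is that the parenthesis is a drafting remnant. Its own sentence names vaccine and placebo recipients, the next sentence puts FLSC in all three arms, Table 3 fixes the allocation, and 13.2 and 13.5 give the contrast without arm numbers. That stands: a competent analyst would recover the intent. The written instruction is still wrong.

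Several stronger readings are tempting but not supported.

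- **A large loss of power against placebo.** A reader might combine the words with the arm numbers and infer a test of 30 vaccinees in Arms 1 and 2 against the 5 placebo recipients in Arm 3. With assumed response of 50% in vaccinees and 2% on placebo, Fisher power would be 39%, against 99% for 45 versus 15. No section states that contrast, and at 80% response its power is already 98%. It is one possible reading and not the size of this point.
- **p<0.05 as the dose-selection rule.** Section 12.2.5 bases dose choice on CD4i immunogenicity, antiviral activity and safety, not on a p-value.
- **No two-group test in the plan.** Section 12.2.5 does name a rank-sum test if normality fails. The gap is narrower: there is no pairwise step after ANOVA, and the claim that a dose is higher is not tied to any pairwise result.
- **The wrong dose would usually be picked.** The simulation does not show this. In the 0/0.6/0.6 pattern the top-ranked dose separates from both others in about 5% of significant trials, but that figure is largely built in, because the two top doses are equal.

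The arm count in 4.2 may mean three arms that each include placebo, and the Figure 1 reference in 6.1 is a slip. Both are editorial.

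**Conclusion.** The concern holds for three statements in the secondary immunogenicity analysis.

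1. The parenthesis in 12.2.5 does not describe vaccine against placebo. Taken literally, it has 25% placebo on each side and the placebo mean cancels. This follows from the allocation alone, given a common placebo mean.
2. The p<0.05 sentence claims more than an overall test can show. Its practical weight depends on the dose-response shape. It misleads most when two doses are similar, and the likely harm is a claim of superiority over a similar dose. The 92% and 96% figures rest on assumed means, SD 0.5 and normal log titers.
3. The paired test in 13.5 has no pairs to work on.

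The primary safety analysis and the sample size are untouched. The intended contrast is recoverable, except that 13.2 and 13.5 do not say whether placebo is pooled across groups or taken within group; section 13.1 calculates both for safety. The correction is to wording, and should be made before the data are analysed.

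**What to change.** 1. **12.2.5, contrast.** Delete the parenthesis that equates vaccine versus placebo with arm numbers. Name the groups: vaccinees at 75, 150 and 300 ug (15 each) and placebo recipients (15). State that the placebo comparator is pooled: 45 versus 15 overall, and each dose (15) versus 15. Show per-group placebo results as well, because the groups enrol in sequence.
2. **12.2.5, placebo arm pairs.** If this is meant as a check of placebo recipients across groups, say so; otherwise delete it.
3. **12.2.5, 13.2 and 13.5, tests.** Use one set. For response, Fisher's exact test in place of chi-square. For titers, t test or ANOVA on log titer, with rank-sum or Kruskal-Wallis under the normality rule already in 12.2.5. Keep paired tests only for within-volunteer change.
4. **12.2.5, p-value sentence.** Replace it: the overall test shows a difference among doses, and any statement that a dose is higher rests on pairwise differences in log titer with 95% confidence intervals. A multiplicity adjustment is optional.
5. **13.6.** Say whether 0.05, used in 12.2.5 and 13.4, applies to these comparisons or whether they are descriptive.
6. **Tidy in the same edit.** In 4.2, describe three dose groups, each with vaccine and placebo recipients. In 6.1, refer to Table 3.

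**Cost.** No new samples, assays or volunteers. The main drawback is that pairwise intervals at 15 per dose are wide (half-width about 0.37 log10 at assumed SD 0.5), so the trial may be unable to call one dose higher. If Holm's adjustment over three pairs is chosen, power for an assumed 0.6 log10 difference between 75 and 300 ug falls from about 89% to 77–81%. Pooling placebo mixes sequentially enrolled groups, hence the per-group display.
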